11.4 Beck Depression Inventory II

Descriptive summaries (mean, SD, median, minimum, and maximum) of actual values and changes from baseline at each assessment time point and last available assessment will be calculated for the BDI-II total score. 95% confidence intervals will be presented for change from baseline.

These summaries will be presented by treatment and assessment time for the Safety population. ET data will be analyzed with the closest visit that does not have a valid assessment value.

Protocol: TNX-CY-F307 Page 34 of 45

Final v1.0

11.5 Vital Signs

Descriptive summaries (mean, SD, median, minimum, and maximum) of actual values and changes from baseline at each assessment time point and last available assessment will be calculated for vital signs including weight, BMI, body temperature, pulse rate, systolic blood pressure and diastolic blood pressure. 95% confidence intervals will be presented for change from baseline.

These summaries will be presented by treatment and assessment time for the Safety population. ET data will be analyzed with the closest visit that does not have a valid assessment value.

11.6 Physical Examination and Oral Cavity Exam

A standard physical examination will be performed at Screening, Baseline, and Week 14. In addition, a separate examination of the oral cavity will be performed at each visit (Screening through Week 14). Oral cavity examination findings will be documented separately from other physical examination findings. Note that the oral exam did not include examination of the pharynx; any findings there would be recorded with the physical exam, and also on the AE page, if appropriate.

A data listing of the results at each scheduled visit will be presented for both the standard physical examination and the examination of the oral cavity.

Protocol: TNX-CY-F307 Page 35 of 45

Final v1.0

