11.2.2. Baseline Visit

For patients who have qualified for randomization, these assessments and procedures will be completed in the following general order:

- Confirm patient's eligibility based on the diary data collected during the preceding 7 days
- Review completed diary data with the patient and have the patient complete training on how to accurately report pain and reduce placebo response.
- Update medical history (with any changes noted since screening)
- Assess changes in medication history and concomitant medications
- Have the patient complete the BDI-II. If the BDI score is >24, the patient is not eligible for randomization and should be screen failed. In addition, a score > 1 on item #9 (suicidal ideation) is exclusionary.
- Administer the "Since Last Visit" version of the C-SSRS. Any patient exhibiting Type 3, 4, or 5 suicidal ideation or any suicidal behavior since the Screening visit should be screen-failed and assessed for appropriate follow-up care.
 - a. Results of the C-SSRS and BDI-II should be reviewed together to ensure (1) the patient is not experiencing suicidal ideation or worsening depression that requires intervention and (2) both scales are providing a consistent clinical picture of the patient with regard to suicidality.
- Assess occurrence of adverse events
- Conduct a brief physical examination, including vital signs and weight
- Conduct a visual examination of the oral cavity. This examination should include a
 careful visual examination of the sublingual area, tongue, buccal mucosa, lips, palate
 and gums. Any abnormalities should be noted on the oral exam source document. It
 is recommended that both non-significant as well as significant findings be noted so
 that there is a complete and accurate baseline assessment available for comparison to
 findings at later visits.
- Perform urine pregnancy test (for women of child-bearing potential)
- Patient should complete the following patient-reported outcomes (PRO):
 - a. FIQR
 - b. Clinic administered assessment of pain by both 24-hour and weekly recall using 11-point (0-10) NRS scale

- c. PROMIS scales for sleep disturbance and fatigue
- d. CSFQ-14 female or male version, as appropriate
- Ensure that all PROs were accurately and fully completed
- Once it has been confirmed that the patient remains eligible, randomize patient via IRT Randomization System
- Dispense bottle of double-blind study drug as assigned via the IRT

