13.5. Safety Analyses

Safety analyses will be performed using the Safety Population. The analysis of safety assessments in this study will include summaries of the following safety and tolerability data collected for each patient:

- Incidence of Adverse Events
- Changes from baseline in clinical laboratory tests
- Changes from baseline in vital signs
- Changes from baseline in physical examination findings including examination of the oral cavity
- Monitoring suicidality using the C-SSRS
- Changes from baseline in BDI-II scores

All AEs, treatment-emergent adverse events (TEAE), and serious adverse events (SAE) will be coded using the MedDRA.

An AE summary table will be presented for the following:

- All TEAEs
- TEAEs by severity
- TEAEs leading to study drug discontinuation
- TEAEs by relationship
- SAEs
- Oral cavity TEAEs
- Oral cavity TEAEs by severity

Summaries of incidence rates (frequencies and percentages), of individual AEs by MedDRA SOC and preferred term will be prepared. Such summaries will be displayed for all TEAEs, oral cavity TEAEs, TEAEs by maximum severity, and TEAEs by strongest relationship to study drug.

Each patient will be counted only once within each summation level (SOC; preferred term). If a patient experiences more than one TEAE within each summation level, the TEAE with the strongest relationship or the maximum severity, as appropriate, will be included in the summaries of relationship and severity.

In the AE data listings, all AEs will be displayed.

Laboratory data include analytes for Chemistry and Hematology, and these will be summarized by treatment and visit for the Safety Population. Descriptive summaries of actual values and changes from baseline will be presented by study visit and last on-treatment assessment for each clinical laboratory analyte and each treatment group. 95% confidence intervals will be presented for change from baseline.

Laboratory values will be displayed in the data listings with their corresponding normal ranges, and those values that are outside the normal range will be flagged. For each laboratory analyte, shifts in assessments of abnormality from baseline to each scheduled time point will be presented in shift tables.

A by-patient listing of all clinical laboratory data will also be provided.

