Descriptive summaries (mean, SD, median, minimum, and maximum) of actual values and changes from baseline at each assessment time point and last on-treatment assessment will be calculated for vital signs including weight, BMI, body temperature, pulse rate, systolic blood pressure and diastolic blood pressure. 95% confidence intervals will be presented for change from baseline.

Based on the C-SSRS results, the overall number of patients with lifetime and/or current suicidal ideation (by item and category), suicidal behavior (by item and category), or self-injurious behavior at the screening and baseline visit will be summarized by visit and treatment group. Additionally, the overall number of patients with any suicidal ideation or behavior (by type and in total) or self-injurious behavior while on-treatment will be provided by treatment group. Patients will only be counted once for on-treatment at the worst-case response for each item.

Physical examination data and oral examination data will be presented in data listings.

Descriptive summaries (mean, SD, median, minimum, and maximum) of actual values and changes from baseline at each assessment time point and last on-treatment assessment will be calculated for BDI-II scores. 95% confidence intervals will be presented for change from baseline.

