9.3 Demographics and Other Baseline Characteristics

Descriptive summaries of the demographic and other baseline characteristics will be completed for all enrolled patients in the study population by treatment groups, unless otherwise specified.

Descriptive summaries of demographic and other baseline conditions will include:

- Demographics (age, gender, race/ethnicity, height, weight, BMI, family status, education and employment status)
- Tobacco/nicotine, alcohol, and THC/cannabis use history

Medical History will be coded using version 23.0 of the Medical Dictionary for Regulatory Activities (MedDRA) and summarized by SOC and Preferred Term using frequency counts by treatment group. Physical examination data, as well as findings from dedicated oral cavity examinations, will be presented in listings.

Protocol: TNX-CY-F307 Page 26 of 45

Final v1.0

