11. SAFETY AND TOLERABILITY ANALYSES

The safety analyses will be run on the Safety population. The analysis of safety in this study will include summaries of the following safety and tolerability data collected for each patient:

- Adverse Events
- Clinical Laboratory Investigations
- C-SSRS
- BDI-II
- Vital Signs
- Physical Examinations and examinations of the oral cavity
- CSFQ-14

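### Both documents name the oral cavity examination among the safety data to be summarized but plan only listings, so examination findings not entered as adverse events get no by-arm count or change from baseline.

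*SAP*

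**What the plan says.** Each document speaks to the oral examination in two ways.

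**Opening lists.** Protocol 13.5 begins: "The analysis of safety assessments in this study will include summaries of the following safety and tolerability data collected for each patient". One item on its list is "Changes from baseline in physical examination findings including examination of the oral cavity". SAP 11 opens its safety section with a similar promise of summaries and lists "Physical Examinations and examinations of the oral cavity".

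**Specific sentences.** Later in Protocol 13.5: "Physical examination data and oral examination data will be presented in data listings". SAP 9.3: "Physical examination data, as well as findings from dedicated oral cavity examinations, will be presented in listings". SAP 11.6: "A data listing of the results at each scheduled visit will be presented", for both the standard physical examination and the oral examination. No count, shift table or by-arm contrast of examination findings appears anywhere.

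**Why and how the data are collected.** SAP 11.1.3 ties the oral examination to the sublingual route. Protocol 12.3.6 requires examiners trained and certified by the sponsor and schedules the examination at Visits 1 to 6. Protocol 11.2.2 recommends noting non-significant as well as significant findings at baseline, to leave a "complete and accurate baseline assessment available for comparison to" findings at later visits.

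**The adverse event route.** SAP 11.1.3 states that oral cavity AEs may be reported by the patient, seen at an oral examination, or both, and that a CRF question identifies them. SAP 11.1 tabulates oral cavity treatment-emergent AEs overall, by severity, and by system organ class and preferred term. SAP 8.1 says tables are in general by treatment group.

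**The concern.** The examination is a listed safety endpoint (Protocol 7.2.4), safety is the secondary objective, and a baseline examination is taken against which later ones can be read. The plan names a change-from-baseline summary and then specifies none.

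Whether an examination finding reaches a table by arm therefore depends on whether the site entered it as an AE. A mucosal change described on the oral examination source document but judged not to be an AE would appear only in a patient-level listing. From a listing a reader cannot readily see how many patients per arm had a new finding, out of how many examined, or whether the arms differ. The contrast between arms on a route-specific safety measure would then rest wholly on AE entry.

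**Working it through.** No arithmetic applies: the documents attach no rate, hypothesis or sample size to oral findings. The check is a reading of the sections against each other.

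1. **Is a summary of the examination planned anywhere?** SAP 11 lists seven kinds of safety data. Six have tabulated results: AEs (11.1), laboratory values with shift tables (11.2), C-SSRS counts by arm (11.3), BDI-II (11.4), vital signs (11.5) and CSFQ-14 (10.3). The seventh, physical and oral examinations, has a listing only (11.6). Protocol 13.5 lists six kinds; five have a described summary and examinations again have only a listing. In both documents the examinations are the single item whose named summary is not delivered.

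2. **Where does the conflict lie?** SAP 11.6 and 9.3 agree with the listing sentence in Protocol 13.5. The conflict is between the opening list and the specific sentence within each document.

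3. **Do the AE tables carry examination findings?** In part.
   - Protocol 14.1 defines an AE broadly enough to include an unfavorable sign without symptoms.
   - Protocol 12.3.1 requires observed AEs to be recorded.
   - SAP 11.1.3 expressly includes those seen at an oral examination.
   - Findings entered this way reach by-arm tables.

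4. **Do they carry all of them?** Not by rule. Protocol 11.3, 11.4 and 11.5 direct abnormalities to the oral examination source document, and Protocol 12.3.2 asks that findings be noted. None of these, nor 12.3.6, says that a new or worsened oral finding is to be entered as an AE. For laboratory values Protocol 12.3.7 does say that clinically significant abnormalities after Screening are recorded as AEs, and SAP 11.2 still gives shift tables. SAP 11.6 also treats the examination record and the AE page as separate: pharyngeal findings go on the AE page only where appropriate.

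5. **Are unscheduled examinations covered?** Protocol 11.7 and 12.3.6 provide for unscheduled oral examinations when a patient reports an oral event. SAP 11.6 refers to scheduled visits, so read literally its listing leaves out examinations prompted by a reported lesion. The other two listing sentences carry no such limit.

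6. **What is the right denominator?** Protocol 12.3.6 omits the oral examination at telephone visits, so the number examined can be smaller than the number in the arm at any visit.

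**The case against.** The strongest reply is that the AE rules already do this work. An unfavorable mucosal sign is an AE by definition with or without symptoms, observed AEs must be recorded, and oral cavity AEs get tables of their own. What remains outside is findings judged not unfavorable, or under-recording, which is a matter of conduct rather than of the analysis plan. The baseline recommendation may simply help the examiner decide what is new. Findings are descriptive and no graded scale is shown, so a listing is a defensible format.

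Much of this stands. A reader might infer that changes detected at examination are never compared between arms, or that the examinations contribute to no table. The documents do not support either inference, because examination-detected AEs are tabulated by arm. A reader might also infer that the SAP departs from the protocol. It does not: it follows the protocol's own listing sentence.

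What the reply leaves open is the summary that both opening lists name. Whether a finding counts as an AE is a judgment made site by site. Laboratory data have an explicit AE-recording rule and are still summarized directly, so the existence of an AE route is not, in this plan's own practice, a reason to omit a summary.

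**Conclusion.** The point holds in a limited form. Both documents name a summary of the oral examination and neither plans one. The consequence is confined to examination findings not entered as AEs, which get no by-arm count or change from baseline, and to unscheduled examinations if SAP 11.6 is read literally.

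The number of such findings cannot be estimated from the documents, and any power statement would rest on assumed rates for a comparison that carries no planned test. Primary and secondary efficacy inference, alpha and sample size are unaffected.

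This is a cheap improvement to safety reporting, not a defect that threatens the trial's conclusions. It assumes that the findings to be listed are already in the database, as the planned listings imply, and that no unseen instruction requires every new or worsened oral finding to be entered as an AE. If such an instruction exists, the gap shrinks to the wording conflict.

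**What to change.** In SAP 11.6 add one descriptive table by treatment arm:

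- number and percentage of patients with a new or worsened oral examination abnormality relative to the Visit 2 examination;
- at each post-dose visit, and at any post-dose examination, scheduled or unscheduled;
- patients actually examined as the denominator, shown for each arm and visit;
- risk difference between arms with its 95% CI, and no hypothesis test.

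Keep the patient listing and state that it includes unscheduled examinations. Then reconcile the opening lists of Protocol 13.5 and SAP 11 with the listing sentences in Protocol 13.5, SAP 9.3 and SAP 11.6, so that each examination is described the same way throughout.

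The cost is one table from data already collected. The downside is that free-text findings need simple categories and a definition of new or worsened, both fixed before unblinding. If that point has passed, SAP 2 already requires the table to be identified as post hoc. The change concerns reporting only and alters no examination or treatment rule.

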12. MEDICATIONS

12.1 Concomitant Medication

All medications will be coded using the MAR2020 version of the World Health Organization Drug Dictionary. Prior and concomitant medications will be summarized by treatment group and by the number and percentage of patients taking each medication, classified by using WHO-DD Anatomical Therapeutic Chemical Levels 1 and 3 and preferred term.

Prior medications are defined as medications or therapies initiated prior to the start of the study drug and terminated prior to the start of study drug. Hence, these medications or therapies will have end dates prior to the first dose date of study drug. Concomitant medications are defined as any medications other than the study drug that a patient receives concurrently with the study drug. These medications will have end dates on or after the first dose date of the study drug.

Prior and Concomitant medications will be summarized. All medications will be presented in a listing.

Please refer to Section 8.3 to impute the partial start date and end date of concomitant medication.

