followed by the Baseline/Randomization Visit (Visit 2, Day 1), 4 treatment visits at Weeks 2, 6, 10, and 14 (or Early Termination), and a Week 16 telephone follow-up visit. The total duration of the study, including Screening, will be approximately 17-21 weeks. The maximum treatment duration will be 14 weeks.

Eligible patients who provide written informed consent will have study assessments performed at Screening and will stop all excluded medications during the washout period through the Week 14 visit (Visit 6). Patients will record their average pain intensity for the previous 24 hours in the evening every day from Visit 1 through Visit 6 on an electronic diary system. After recording Baseline Diary scores for at least 7 days, patients will return to the investigative site for Baseline assessments and randomization (Day 1), where they will be randomly assigned to receive TNX-102 SL or matching placebo sublingual tablets in a 1:1 ratio.

Patients will take the study drug sublingually daily at bedtime, starting on the day that they are randomized (Day 1), for 14 weeks. For the first two weeks of treatment, patients will start on TNX-102 SL 2.8 mg (1 tablet) or placebo. Upon return to the site¹ for the Week 2 visit (Visit 3), all patients will have the dose increased to TNX-102 SL 5.6 mg (2 x 2.8 mg tablets) or two placebo tablets. Patients will return to the site¹ for assessment of efficacy and safety, as well as dose tolerability, at Weeks 6, 10, and 14 (or Early Termination). A safety follow-up telephone visit will occur at Week 16.

In scenarios in which TNX-102 SL 5.6 mg, or 2 placebo tablets, is considered intolerable due to adverse event(s) and would otherwise lead to study discontinuation, with Medical Monitor approval, the Investigator may lower the dose back to 1 tablet every night (TNX-102 SL 2.8 mg or one placebo tablet). Re-challenge with 2 tablets TNX-102 SL 2.8 mg (5.6 mg dose)/placebo may be attempted at a later date if/when it is deemed clinically warranted by the Investigator, or the patient may remain on the lower dose for the remainder of the study.

Patients who wish to withdraw from the study may do so at any time.

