11.6. Visit 7 (Week 16/Post-study Safety Follow-up)

Visit 7 should occur approximately 2 weeks -4/ +7 days after Visit 6/ET. This visit will be performed by telephone, to collect any additional data on concomitant medications and AEs and the general condition of the patient.

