8.3 Safety Endpoints

To handle missing or partial AE and concomitant medication dates, the following rules will be applied.

For partial start dates:

- 1. If the year is unknown, then do not impute the date but assign a missing value.
- 2. If the month is unknown, then:
 - a. If the year matches the year of the first dose date, then impute the month and day of the first dose date.
 - b. Otherwise, assign "January."
- 3. If the day is unknown, then:
 - a. If the month and year match the month and year of the first dose date, then impute the day of the first dose date.
 - b. Otherwise, assign "01."

For partial end dates:

- 1. If the year is unknown, then do not impute the date but assign a missing value.
- 2. If the month is unknown, then assign "December."
- 3. If the day is unknown, then assign the last day of the month.

Adverse events are categorized as pre-treatment adverse events or treatment-emergent adverse events based on the response to the CRF question "Did the AE start prior to the first dose?"

The missing severity of an AE will be imputed to "severe"; the missing relationship to study drug of an AE will be imputed to "possibly related".

After implementing the rules above, the following strategy will be used to determine whether medications with missing start or stop dates are prior or concomitant medications:

- 1. If the start date and stop date are both missing, then the most conservative approach is taken and the medication is considered to be a concomitant treatment.
- 2. If the start date is missing but the stop date is not missing and is after the day of first study dose administration, then the most conservative approach is taken and the medication is considered to be concomitant.
- 3. If the start date is missing but the stop date is not missing and is on or before the day of first study dose and after the date of signed informed consent, then the medication is considered to be a prior treatment.
- 4. If the start date is not missing but the stop date is missing, then the most conservative

Protocol: TNX-CY-F307 Page 24 of 45

Final v1.0

approach is taken and the medication is considered to be concomitant.

Protocol: TNX-CY-F307 Page 25 of 45

Final v1.0

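### The SAP's date rules for concomitant medication never test whether a drug started by the last dose, so drugs begun after treatment can be counted as concomitant

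*SAP*

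**What the plan says.** SAP 12.1 sorts medications into two classes. Prior medications begin and finish before study drug, and the date form is: "Hence, these medications or therapies will have end dates prior to the first dose date of study drug". For the second class it says: "Concomitant medications are defined as any medications other than the study drug that a patient receives concurrently with the study drug". The date form follows directly: "These medications will have end dates on or after the first dose date of the study drug". Both classes are summarised by treatment group, and all medications are listed. No third class is named.

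SAP 8.3 adds rules for incomplete dates, applied after partial dates have been imputed. Three matter here:

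- Rule 2: "If the start date is missing but the stop date is not missing and is after the day of first study dose administration", the medication is concomitant.
- Rule 3 gives prior for this case: "If the start date is missing but the stop date is not missing and is on or before the day of first study dose", provided the stop is later than consent.
- Rule 4: "If the start date is not missing but the stop date is missing", the medication is concomitant, described as the conservative choice.

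Medication data continue after dosing. Protocol 11.6 sets a telephone Visit 7 about 2 weeks (-4/+7 days) after Visit 6 or early termination, in part "to collect any additional data on concomitant medications and AEs". Protocol 11.5.2 records medications at the early termination visit, accepts that this visit may come after a lapse in study drug, and gives those patients the follow-up call as well.

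**The concern.** The definition in 12.1 implies two limits: the drug must not have ended before study drug began, and must not have begun after study drug ended. The date rules carry only the first limit. A programmer who codes the dates as written will call a drug concomitant even if its first dose came after the patient's last study tablet.

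The table at stake is the by-arm summary of concomitant medication. Readers will look there to see which analgesics, antidepressants or hypnotics were taken alongside study drug. Drugs begun afterwards would suggest on-treatment use that did not occur. They would also inflate the apparent number of patients exposed to study drug together with antidepressants of the kind for which Protocol 9.1 asks for a caution about serotonin syndrome.

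A smaller inconsistency lies at the other end. A stop date on the first-dose day is treated one way in 8.3 rule 3 and the other way in 12.1.

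**Working it through.** The plan gives no figure to reproduce. The check is to apply each rule to typical records on the nominal schedule.

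**Inputs.** First dose is Day 1 and last dose is Day 98 (dosing days in the Protocol Synopsis and SAP 4.2). Visit 6 is Day 99 and Visit 7 is Day 113 with a window of -4/+7 days (Protocol Table 2).

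**Rules.** Definition (12.1): taken concurrently with study drug. Date criterion (12.1): end day ≥ 1 is concomitant, end day < 1 is prior. Rule 3 (8.3): start missing and stop day ≤ 1, after consent, is prior. Rule 4 (8.3): start known and stop missing is concomitant.

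| Record | By the 12.1 definition | By the date rules |
|---|---|---|
| A. Start Day -60, stop Day -10 | Prior | Prior (12.1) |
| B. Start Day 40, stop Day 50 | Concomitant | Concomitant (12.1: 50 ≥ 1) |
| C. Start Day 101, stop Day 110 | Neither; it begins after Day 98 | Concomitant (12.1: 110 ≥ 1) |
| D. Start Day 101, no stop date | Neither; it begins after Day 98 | Concomitant (8.3 rule 4) |
| E. Start missing, stop Day 1 | Not settled by the definition | Concomitant by 12.1 (1 ≥ 1); prior by 8.3 rule 3 |

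A and B agree. C and D meet the date rules and fail the definition. D is the pattern of a drug begun after treatment and still in use at the follow-up call. Nothing about D is uncertain in the relevant sense: the start date is known and is later than the last dose. E is a direct conflict. Two patients who both stopped a drug on Day 1 fall into different classes according to whether the start date was recorded, because only the record without a start date reaches rule 3.

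**Length of the exposed interval.**

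- Nominal: Days 99 to 113 = 113 - 99 + 1 = 15 days.
- Earliest Visit 7: Day 113 - 4 = 109, so 109 - 99 + 1 = 11 days.
- Latest Visit 7: Day 113 + 7 = 120, so 120 - 99 + 1 = 22 days.
- After early termination, any lapse between the last dose and the termination visit is added.

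**Is there another class for C and D?** No. SAP 12.1 plans prior and concomitant summaries only. SAP 11.1 does plan a summary of post-treatment adverse events, so the SAP recognises the post-treatment period for events but not for medications.

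**The case against.** The strongest reply is that 12.1 opens with the right definition. On that reading the end-date sentence describes drugs already known to be concurrent and is not a complete test, so a careful programmer would exclude C. This stands in part. A reader might infer that the SAP plans to tabulate every later drug as concomitant, and the definition does not support that inference. What remains is that the end-date sentence is the only date criterion given, and the parallel sentence for prior medications is worded as the date form of its definition.

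Rule 4 can be defended as a conservative default for missing data. That justifies assuming a drug continued when its stop date is unknown, but not ignoring a start date that is known. The SAP does not say whether a drug recorded as ongoing counts as having a missing stop date. This does not rescue the rule, because such a drug cannot meet the 12.1 criterion for prior either.

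A reader might also infer that many patients will restart prohibited pain drugs before Visit 7 and appear as violators. The documents do not support this. They are mixed on when excluded drugs may be resumed: the Synopsis and Protocol 7.1 bar them through Week 14, while inclusion criterion 6 (Protocol 8.2) requires withdrawal for the whole study, which 7.1 describes as 16 weeks. Those texts need reconciling, but the present point does not depend on them, since it applies to any drug begun after the last dose. Neither a washout rate nor a restart rate is given. Guesses of 30-60% washed out and 25-75% restarting give 470 × 0.30 × 0.25 = 35 to 470 × 0.60 × 0.75 = 212 patients, a six-fold range set wholly by the guesses. The table is also organised by drug class and preferred term, not by prohibited status.

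Finally, confounding by concomitant drugs is addressed elsewhere. Opioid records are reviewed and flagged before lock (SAP 4.4.1, 12.2), the opioid sensitivity analysis works by day of use (10.1.3), deviations are summarised by arm (9.2), and all medications are listed. This stands, and it limits the consequence.

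**Conclusion.** The point holds as an incomplete date rule that conflicts with its own definition. Applied literally, SAP 12.1 and 8.3 rule 4 place medications begun after study drug ended in the by-arm concomitant medication table. This assumes that the dates are programmed as written and that some patients start a drug between the last dose and the last contact, a nominal interval of 15 days.

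The number of affected patients cannot be estimated from the documents. Whether it would differ between arms is equally unknown; a reader might infer a difference from unequal dropout, but no figure supports it. The error is confined to a descriptive table. No primary, key secondary or sensitivity analysis uses the prior or concomitant label, so efficacy inference is untouched.

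The disagreement over a stop on the first-dose day is definite but minor. It needs a missing start date and a stop on exactly that day.

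**What to change.** - In SAP 12.1, define concomitant as: start on or before the last dose date (or start missing), and end on or after the first dose date (or ongoing, or stop missing).
- Define post-treatment as a start after the last dose date. Keep these records out of the concomitant table and list or tabulate them separately.
- Add the same start-date condition to 8.3 rule 4. Apply it after the partial-date imputation already specified there.
- Use one boundary for a stop on the first-dose day. Keeping the 12.1 boundary means only moving that day from rule 3 to rule 2.

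Records C and D then become post-treatment (101 > 98), A and B are unchanged, and E has one class. The cost is a few sentences of SAP text and one programming condition. Medication dates are already recorded, and SAP 12.3 already uses the last dose date for treatment duration, so no new data are needed.
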